6.10.1. Primary Outcome and Methodology

The primary outcome is the proportion of patients achieving treatment success, defined as achieving ASAS40 at Week 16 (Visit 8) and remaining on the initially randomized treatment. This is a de-facto effectiveness estimand (that is, the relative effect attributable to the originally randomized treatment, ixekizumab and placebo, at the primary time point of Week 16 in all treated patients). With this estimand, any patient who discontinues treatment before Week 16 is considered a treatment failure through the use of the NRI. The numeric result for treatment success/failure is identical to NRI but interpreted differently and has different consequences for missing data. With NRI, as the acronym implies, there is explicit imputation of missing ASAS40 outcomes. With treatment success/failure, discontinuation of study medication is considered a treatment failure because if patients cannot adhere to the medication, they will not have sustained benefit from it. Therefore, every patient will have an observation for treatment success/failure, and there will be no missing data for this estimand and hence inferences will not depend on missing data assumptions. These attributes also apply to other endpoints involving use of NRI.

The primary outcomes related to improvement in symptomatic features of axSpA are assessed at Week 16 (Visit 8) before placebo patients being rerandomized to ixekizumab during Period 3 (Extended Treatment Period).

The primary analysis will be based on the ITT Population for the Blinded Treatment Dosing Period (Period 2) comparing each ixekizumab treatment group and placebo at Week 16 (Visit 8). The primary analysis is a logistic regression analysis with treatment, geographic region, number of prior TNF inhibitors used, and baseline CRP status in the model (Section 6.1.1).

In the primary analysis, treatment groups of ixekizumab 80 mg Q2W and Q4W will be analyzed without regard to starting dose. The primary comparison will be tested based on the graphical multiple testing procedures detailed in Section 6.5.

[Table RHBW.6.5](#) provides the detailed analyses including analysis type, method and imputation, population, time point, and treatment comparisons for the primary outcome.

6.10.2. Major Secondary Efficacy Analyses

The major secondary outcomes at Week 16 (Visit 8) are:

- Proportion of patients achieving an ASAS20 response
- Change from baseline in ASDAS
- Change from baseline BASDAI
- Change from baseline in BASFI
- Proportion of patients achieving ASDAS <2.1
- Change from baseline in SF-36 PCS*
- Change from baseline in ASAS HI*
- Change from baseline in MRI SPARCC spine score

* Detailed descriptions and analyses on SF-36 PCS and ASAS HI are described in [Table RHBW.6.6](#) and [Table RHBW.6.7](#).

The major secondary analysis will be based on the ITT Population for the Blinded Treatment Dosing Period (Period 2) comparing each ixekizumab treatment group and placebo at Week 16 (Visit 8). In the major secondary analyses, treatment groups of ixekizumab 80 mg Q2W and Q4W will be analyzed without regard to starting dose.

The primary analysis for categorical major secondary outcomes is a logistic regression analysis with treatment, geographic region, number of prior TNF inhibitors used, and baseline CRP status in the model (Section 6.1.1). Missing data will be imputed using the NRI method (Section 6.3.1).

The primary analysis for continuous major secondary outcomes (except MRI SPARCC spine score) is a MMRM analysis with treatment, geographic region, number of prior TNF inhibitors used, baseline CRP status, baseline value, visit, baseline value-by-visit, and treatment-by-visit interaction as fixed factors (Section 6.1.1).

The primary analysis for change from baseline in MRI SPARCC score is an observed case analysis using ANCOVA with treatment, geographic region, number of prior TNF inhibitors used, baseline CRP status, and baseline value in the model (Section 6.1.1). Only patients with both baseline and Week 16 MRI SPARCC spine score will be included in the analysis.

These major secondary comparisons will be tested based on the graphical multiple testing procedure detailed in Section 6.5.

Table RHBW.6.5 provides the detailed analyses including analysis type, method and imputation, population, time point, and treatment comparisons for major secondary outcomes.

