As a secondary analysis for the primary and major secondary categorical efficacy measures, a categorical mixed-effects model of repeated measures (categorical MMRM) estimating the percentage of patients achieving response across postbaseline visits may be used. The model will include treatment, geographic region, baseline CRP status, number of prior TNF inhibitors used, visit, and treatment-by-visit as fixed factors, as well as the continuous, fixed covariate of baseline value and baseline value-by-visit interaction (when appropriate). The binomial distribution and the logit link will be used. An unstructured covariance matrix will be used to model the within-patient variance-covariance errors. The Kenward-Roger approximation will be used to estimate the denominator degrees of freedom. The Newton-Raphson with ridging optimization technique will be used to aid with convergence. The probability of response, the corresponding 2-sided 95% CI, and the p-value for treatment comparisons at Week 16 (Visit 8) and all other postbaseline visits will be reported.

If the unstructured covariance matrix results in a lack of convergence, the heterogeneous Toeplitz covariance structure, followed by the heterogeneous autoregressive covariance structure, followed by the compound symmetry, will be used. This order is specified according to a decreasing number of covariance parameters in the structure. The sandwich estimator (Diggle et al. 1994) for the covariance estimation will be used by specifying the EMPIRICAL option in SAS PROC MIXED. When sandwich estimation is used, the Kenward-Roger approximation for denominator degrees of freedom cannot be used. Instead, the DDFM=BETWITHIN option will be used to estimate denominator degrees of freedom.

The primary analyses for continuous efficacy and health outcomes variables will be made using MMRM. A secondary analysis for continuous efficacy and health outcomes variables will be made using analysis of covariance (ANCOVA).

When the MMRM is used, the model will include treatment, geographic region, baseline CRP status, number of prior TNF inhibitors used, baseline value, baseline value-by-visit, visit, and treatment-by-visit interaction as fixed factors. The covariance structure to model the

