As a secondary analysis for the primary and major secondary categorical efficacy measures, a categorical, pseudo-likelihood based mixed-effects model of repeated measures (categorical mixed-effects model of repeated measures [MMRM]) estimating the percentage of patients achieving response across postbaseline visits may be used. The model will include treatment, geographic region, number of prior TNF inhibitors used, baseline CRP status, visit, and treatment-by-visit as fixed factors. The binomial distribution and the logit link will be used. The restricted maximum likelihood (REML) will be used. An unstructured covariance matrix will be used to model the within-patient variance-covariance errors. The Kenward-Roger approximation will be used to estimate the denominator degrees of freedom. The Newton-Raphson with ridging optimization technique will be used to aid with convergence. The probability of response, the corresponding 2-sided 95% CI, and the p-value for treatment comparisons at Week 16 (Visit 8) and all other postbaseline visits will be reported.

If the unstructured covariance matrix results in a lack of convergence, the heterogeneous Toeplitz covariance structure, followed by the heterogeneous autoregressive covariance structure, followed by the compound symmetry will be used. This order is specified according to a decreasing number of covariance parameters in the structure. The sandwich estimator (Diggle et al. 1994) for the covariance estimation will be used by specifying the EMPIRICAL option in SAS PROC MIXED. When sandwich estimation is used, the Kenward-Roger approximation for denominator degrees of freedom cannot be used. Instead, DDFM= BETWITHIN option will be used to estimate denominator degrees of freedom.

The primary analyses for continuous efficacy and health outcomes variables will be made using MMRM, except for magnetic resonance imaging (MRI) endpoints, which will be made using analysis of covariance (ANCOVA). A secondary analysis for continuous efficacy and health outcomes variables will be made using ANCOVA.

When the MMRM is used, the model will include treatment, geographic region, number of prior TNF inhibitors used, baseline CRP status, baseline value, visit, baseline value-by-visit, and

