6.2. Adjustments for Covariates

The countries will be categorized into geographic regions for statistical analysis (Table RHBW.6.3). Unless otherwise specified, the statistical analysis models will adjust for geographic region, baseline CRP status (nonelevated or elevated), and number of prior TNF inhibitors used (1 or 2).

Below are the initial country allocations.

Table RHBW.6.3. Geographic Regions for Statistical Analysis

Geographic Region	Country or Countries
Non-Europe	United States, Canada, Mexico, Korea, Argentina, Israel, Brazil
Europe	Finland, France, Poland, Germany, Italy, Spain, UK, The Netherlands

In general, when an MMRM is to be used for analyses, baseline value and baseline-by-visit interactions will be included as covariates; when an ANCOVA is to be used for analyses, baseline value will be included as a covariate.

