6.5. Multiple Comparisons/Multiplicity

A multiple testing strategy for the primary and major secondary objectives will be implemented to control the family-wise type I error rate at a 2-sided α level of 0.05. The primary outcome will be tested by using the primary analysis method, logistic regression analysis with treatment, geographic region, number of prior TNF inhibitors used, and baseline CRP status in the model, with NRI missing data imputation approach.

A graphical multiple testing procedure (Bretz et al. 2011) will be used (Figure RHBW.6.1). The graphical approach is a closed testing procedure; hence, it strongly controls the family-wise error rate (Alosh et al. 2014). The following is a list of primary and major secondary outcomes to be tested for both ixekizumab 80 mg Q2W and Q4W regimen at Week 16:

- Primary - proportion of patients achieving an ASAS40 response [ASAS40]
- Secondary 1 - proportion of patients achieving an ASAS20 response [ASAS20]
- Secondary 2 - change from baseline in ASDAS score [ASDAS change from baseline (CFB)]

- Secondary 3 - change from baseline in BASDAI score [BASDAI CFB]
- Secondary 4 - change from baseline in BASFI [BASFI CFB]
- Secondary 5 - change from baseline in SF-36 PCS score [SF-36 PCS CFB]
- Secondary 6 - proportion of patients achieving ASDAS <2.1 [ASDAS<2.1]
- Secondary 7 - change from baseline in ASAS Health Index (ASAS HI) [ASAS HI CFB]
- Secondary 8 - change from baseline in MRI of the spine [MRI spine SPARCC score CFB]

With the exception of secondary outcome 8 (MRI spine SPARCC score CFB), the remaining secondary outcomes are grouped into 2 tiers ([Figure RHBW.6.1](#), [Figure RHBW.6.2](#), and [Figure RHBW.6.3](#)) based on the clinical importance as well as statistical significance observed in historical axSpA studies.

[Figure RHBW.6.1](#) shows the graphical testing scheme with initial α allocation and weights, and [Figure RHBW.6.2](#) and [Figure RHBW.6.3](#) show the graphical testing schemes used within the Tier 1 and Tier 2 groups of endpoints respectively. The testing steps are outlined below:

[figure not shown]
Step 1: The primary outcome of ASAS40 will be tested for ixekizumab 80 mg Q2W versus placebo at a 2-sided $\alpha=0.05$. If the null hypothesis is not rejected, no further testing is conducted as the α for that test is considered ‘spent’ and cannot be passed to other endpoints. If the null hypothesis is rejected, then move to Step 2.

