Step 2: The primary outcome of ASAS40 will be tested for ixekizumab 80 mg Q4W versus placebo at a 2-sided $\alpha=0.05$. If the null hypothesis is not rejected, no further testing is conducted as the α for that test is considered ‘spent’ and cannot be passed to other endpoints. If the null hypothesis is rejected, then move to Step 3.

Step 3: $\alpha=0.025$ will be distributed to Tier 1 set of secondary outcomes for ixekizumab 80 mg Q2W (blue circles in [Figure RHBW.6.2](#)), and the remaining $\alpha=0.025$ will be distributed to Tier 1 set of secondary outcomes for ixekizumab 80 mg Q4W (green circles in [Figure RHBW.6.2](#)).

[figure not shown]
The major secondary endpoints for both doses will be tested according to the procedure specified by the graphs.

The testing process continues for the remaining outcomes by allocating the remaining α to the next set of outcomes as long as at least 1 hypothesis can be rejected. Each time a hypothesis is rejected, the graph is updated to reflect the reallocation of α , which is considered “recycled” (Alosh et al. 2014). This iterative process of updating the graph and reallocating α is repeated until all major secondary hypotheses have been tested or when no remaining hypotheses can be rejected at their corresponding α level. The weights along the edges for α allocation between ixekizumab 80 mg Q2W and ixekizumab 80 mg Q4W outcomes as well as within each of the tiers are prespecified in [Figure RHBW.6.1](#), [Figure RHBW.6.2](#), and [Figure RHBW.6.3](#).

[figure not shown]
Abbreviations: ASAS = Assessment of Spondyloarthritis International Society; CFB = change from baseline; Q2W = every 2 weeks; Q4W = every 4 weeks; SPARCC = Spondyloarthritis Research Consortium of Canada.

Figure RHBW.6.1. Illustration of graphical multiple testing procedure with initial α allocation and weights.

Abbreviations: ASAS = Assessment of Spondyloarthritis International Society; ASDAS = Ankylosing Spondylitis Disease Activity Score; BASDAI = Bath Ankylosing Spondylitis Disease Activity Index; BASFI = Bath Ankylosing Spondylitis Functional Index; CFB = change from baseline; Q2W = every 2 weeks; Q4W = every 4 weeks; SF-36 PCS = Short Form 36 physical component score.

Figure RHBW.6.2. Graphical multiple testing scheme used within the Tier 1 group of endpoints.

Abbreviations: ASAS HI = ASAS Health Index; ASDAS = Ankylosing Spondylitis Disease Activity Score; CFB = change from baseline; Q2W = every 2 weeks; Q4W = every 4 weeks.

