Ankylosing Spondylitis Disease Activity Score (ASDAS)	The ASDAS is a composite index to assess disease activity in AS (Machado et al 2011a, 2011b; Zochling 2011). The parameters used for the ASDAS (with CRP as acute phase reactant) (Sieper et al. 2009, pg 40): 1) Total back pain (BASDAI question 2) 2) Patient global 3) Peripheral pain/swelling (BASDAI question 3) 4) Duration of morning stiffness (BASDAI question 6) 5) CRP in mg/L	ASDAS _{crp}	ASDAS _{crp} (Sieper et al. 2009, pg 41): $0.121 \times \text{total back pain} + 0.110 \times \text{patient global} + 0.073 \times \text{peripheral pain/swelling} + 0.058 \times \text{duration of morning stiffness} + 0.579 \times \text{Ln}(\text{CRP}+1)$ (Machado et al. 2015). CRP is in mg/liter, the range of other variables is from 0 to 10; Ln represents the natural logarithm. Due to the constraint of CRP, ASDAS _{crp} has a minimum score of 0.6361.	Missing if any of the component is missing. If CRP <2 mg/L or below the limit of detection, then use 2 mg/L in the calculation (Machado et al. 2015).
		ASDAS _{crp} change from baseline - major secondary outcome	Calculated as: observed ASDAS – baseline ASDAS	Missing if baseline or observed value is missing
		ASDAS Disease Activity States	Four (4) disease activity states have been defined by ASAS consensus (Machado et al. 2011c, Machado 2018): 
 • ASDAS <1.3 defines inactive disease • $1.3 \leq \text{ASDAS} < 2.1$ defines low disease activity • $2.1 \leq \text{ASDAS} \leq 3.5$ defines high disease activity ASDAS >3.5 defines very high disease activity.	Missing if observed ASDAS score is missing
		ASDAS <2.1	Defined as ASDAS < 2.1	
		Clinical important improvement	Defined as at least 1.1 unit change in ASDAS from baseline	
		Major improvement	Defined as at least 2.0 unit change in ASDAS from baseline, or reached the minimum of ASDAS score (0.6361) at post-baseline visit	

Description and Derivation of Primary and Secondary Efficacy Outcomes

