		Proportion of patients reaching Good ASAS HI (defined as ASAS HI≤5)	This variable will only be derived for patient with baseline score >5.	Missing if baseline or observed value is missing
Medical Outcomes Study 36-item Short-Form Health Survey	The SF-36 is a 36-item patient-administered measure designed to be a short, multipurpose assessment of health in the areas of physical functioning, role – physical, role – emotional, bodily pain, vitality, social functioning, mental health, and general health. The 2 overarching domains of mental well-being and	8 associated domain scores: • Physical Functioning, • Role Physical, • Bodily Pain, • General Health,	Per copyright owner, the QualityMetric Health Outcomes™ Scoring Software 4.5 will be used to derive SF-36 domain and component scores. After data quality controls, the SF-36 software will re-calibrate the item-level responses for calculation of the domain and component scores. These raw scores will be	Missing data handling offered by SF-36 software will not be used.

Measure	Description	Variable	Derivation / Comment	Imputation Approach if with Missing Components
	physical well-being are captured by the Mental Component Summary and Physical Component Summary scores. The summary scores range from 0 to 100; higher scores indicate better levels of function and/or better health. Items are answered on Likert scales of varying lengths. The SF-36 version 2 (acute version) will be used, which utilizes a 1-week recall period (Ware [2000]).	
 • Vitality • Social Functioning • Role Emotional • Mental Health 2 component Scores: 
 • MCS Score • PCS Score 	transformed into the domain scores (t-scores) using the 1-week recall period. The procedure to derive the SF-36 scores is described in Appendix 6 . It entails exporting the patient data in a CSV or tab-delimited file for import, generation of the SF-36 scores and reports, and export of the calculated scores in a CSV or tab-delimited file for integration into SDTM/ADaM datasets. The summary scores range from 0 to 100.	
		PCS change from baseline-Major Secondary	Calculated as: observed score – baseline score	Missing if baseline or observed value is missing
		MCS and domain scores change from baseline	Calculated as: observed score – baseline score	Missing if baseline or observed value is missing

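### ASDAS <2.1 is tested under alpha control without adjusting for baseline ASDAS: the test is valid, but one covariate already collected could recover some power

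*SAP*

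**What the plan says.** SAP 6.5 lists the proportion of patients with ASDAS <2.1 at Week 16 as the sixth major secondary outcome in the graphical procedure, for each ixekizumab regimen against placebo. The tier figures are not shown. The abbreviation list for Figure RHBW.6.3, "Abbreviations: ASAS HI = ASAS Health Index; ASDAS = Ankylosing Spondylitis Disease Activity Score; CFB = change from baseline", suggests that the endpoint sits in Tier 2.

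Table RHBW.6.4 defines the endpoint by the Week 16 score alone, not by change. It also sets a floor for the score: "If CRP <2 mg/L or below the limit of detection, then use 2 mg/L in the calculation".

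SAP 6.10.2 gives the confirmatory model: "categorical major secondary outcomes is a logistic regression analysis with treatment, geographic region, number of prior TNF inhibitors used, and baseline CRP status", with nonresponder imputation. SAP 6.1.1 specifies a Wald test, with Fisher's exact test if data are too sparse. For the continuous major secondaries, 6.10.2 does include the baseline value.

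For the secondary categorical MMRM the wording varies:

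- Protocol 9.2.1 includes the baseline value and its interaction with visit where appropriate.
- SAP 6.2 says: "In general, when an MMRM is to be used for analyses, baseline value and baseline-by-visit interactions will be included as covariates".
- SAP 6.1.1 omits it: "The model will include treatment, geographic region, number of prior TNF inhibitors used, baseline CRP status, visit, and treatment-by-visit as fixed factors".

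**The concern.** ASAS20 and ASAS40 are defined by improvement from the patient's own baseline. ASDAS <2.1 is not, so starting level enters directly into the chance of response. A patient near the threshold needs little change, and a patient with very high activity needs a large fall. When a covariate predicts the outcome, leaving it out of a logistic model leaves the treatment test valid but usually less powerful.

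The SAP recognises starting level for some other threshold endpoints by restricting the population. For a good ASAS HI (score of 5 or less): "This variable will only be derived for patient with baseline score >5". MASES = 0 is analysed only in patients with baseline MASES above 0. ASDAS <2.1 has neither a restriction nor an adjustment, and none of its listed analyses names baseline ASDAS. What is at stake is some power on one endpoint that carries alpha.

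**Working it through.** **1. The plan's own power figure.** The only readable power statement is in the protocol synopsis: about 96% for ASAS40, 27% vs 7%, 100 per arm, two-sided Fisher's exact test at 0.05. Full enumeration gives 96.5%, so it reproduces. No power is stated for ASDAS <2.1.

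**2. Spread of starting values within one CRP stratum.** The four item weights in Table RHBW.6.4 sum to 0.121 + 0.110 + 0.073 + 0.058 = 0.362. Both patients below meet the entry criteria (BASDAI ≥4, back pain ≥4) and are in the nonelevated stratum (CRP ≤5.00 mg/L).

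- All items 4, CRP at or below 2 mg/L: 0.362 × 4 + 0.579 × ln(3) = 2.084, already below 2.1.
- All items 10, CRP 5.00 mg/L: 0.362 × 10 + 0.579 × ln(6) = 4.657, so a fall of more than 2.5 is needed.

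With the same region and number of prior TNF inhibitors, the model treats these two patients as alike.

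**3. Main simulation.** From the documents: three arms of 100, 60% with CRP >5 mg/L, the SAP covariates and the Fisher fallback. Assumed: baseline ASDAS mean 3.8, SD 0.73, correlation 0.52 with CRP status; 10% dropouts counted as nonresponders; response 5% vs 18% or 7% vs 22%. Both models were fitted to the same 6,000 trials per scenario. The Monte Carlo standard error of a gain is at most about 0.5 points. Local alpha depends on weights that cannot be read, so three values were used.

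Power gain in percentage points from adding baseline ASDAS:

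| Baseline to Week 16 correlation | alpha 0.0125 | alpha 0.025 | alpha 0.05 |
|---|---|---|---|
| 0.2 | 0.7 to 0.9 | 0.5 to 0.6 | 0.1 to 0.6 |
| 0.3 | – | 0.8 to 1.5 | – |
| 0.4 | – | 1.9 to 2.3 | – |
| 0.5 | – | 3.2 (e.g. 74.8% to 77.9%) | – |
| 0.6 | 7.2 to 7.6 | 5.2 to 5.5 (e.g. 80.2% to 85.4%) | 3.2 to 3.9 |

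(A dash means no figure is quoted.)

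Two variations at alpha 0.025, with 4,000 trials each:

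- Sparse rates, 2% vs 10%: gains of 0.8, 2.2 and 6.3 points at correlations 0.2, 0.4 and 0.6. In 13–14% of these trials the test falls to Fisher's exact, where the covariate does nothing.
- CRP status more closely tied to baseline ASDAS (correlation 0.66), 7% vs 22%: the gain at 0.5 drops from 3.2 to 2.3 points.

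**4. Second simulation with other inputs.** 8% dropout; correlation of CRP status with ASDAS 0.4 or 0.7; 4,000 trials per scenario. Power at alpha 0.025, without → with baseline ASDAS, for CRP correlation 0.4:

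| Correlation | 10% vs 25% | 5% vs 17% | 7% vs 27% |
|---|---|---|---|
| 0 | 71.8 → 71.9 | 66.5 → 66.5 | 94.9 → 94.9 |
| 0.3 | 70.8 → 72.4 | 64.5 → 65.5 | 94.7 → 95.4 |
| 0.5 | 71.0 → 76.6 | 67.0 → 71.9 | 95.3 → 96.8 |
| 0.7 | 73.6 → 85.9 | 68.2 → 79.5 | 95.0 → 98.3 |

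At CRP correlation 0.7 the gains are generally smaller (10% vs 25%, correlation 0.5: 74.0 → 77.1). Over all scenarios and alphas the gain runs from none to about 14 points. When baseline ASDAS is not prognostic, nothing visible is lost.

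**5. Type I error, nominal 5%.** Main simulation, 7% in all arms: 4.0% without and 4.1% with the covariate at correlation 0.2; 3.5% and 4.1% at 0.5. Second simulation: 4.4–4.5% without and 4.6–4.9% with. Neither model inflates.

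**The case against.** The strongest reply is that this is a legitimate prespecified choice. SAP 6.2 adjusts for region, CRP status and number of prior TNF inhibitors, which mirror the randomisation strata, and one model serves every categorical endpoint. Good ASAS HI and MASES = 0 go through that same model. Their baseline rules restrict who is analysed; they do not adjust. That distinction is correct, so those endpoints show only that starting level was considered. ASDAS change, also alpha-controlled, already carries baseline ASDAS.

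The 2.08 and 4.66 patients are extremes. Under the assumed distribution, the gap between CRP strata is 0.52 × 0.73 / √(0.6 × 0.4) = 0.775. The nonelevated stratum then has mean 3.8 − 0.6 × 0.775 = 3.34 and SD 0.73 × √(1 − 0.52²) = 0.62. The two patients lie about 2 SD either side of that mean, and on a normal approximation roughly 2% of the stratum would start below 2.1.

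The gain rests on assumed inputs and is small at low correlations. At 7% vs 27%, the planning rates for ASAS40, it is only about 0 to 3 points at alpha 0.025. It also applies only if the test is reached, which requires both ASAS40 tests to succeed and, if the endpoint is in Tier 2, alpha to pass from Tier 1. Version 4 postdates the first unblinding, so a change there cannot add power to the confirmatory test. All of this stands.

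A patient with no baseline ASDAS would drop out of the adjusted model. That should be rare, because baseline is the last value before the first injection and the components are collected at Visits 1 and 2, but a rule is needed. The categorical MMRM wording is a side issue: that analysis is optional, and the qualifiers in protocol 9.2.1 and SAP 6.2 permit the SAP 6.1.1 list.

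None of this removes the point itself: a likely prognostic value already in hand is left out of the test of an absolute threshold.

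**Conclusion.** The concern holds as an optional efficiency point. The prespecified test of ASDAS <2.1 is valid and should not be described as wrong. At alpha 0.025, with response near 5% vs 18% or 7% vs 22%, adding baseline ASDAS is worth about 1 point of power at a baseline-to-Week-16 correlation of 0.3, about 3 at 0.5 and about 5 at 0.6. The gain is larger at a smaller local alpha. It is smaller where power is already high or CRP status tracks ASDAS closely. The correlation, the response rates, the baseline ASDAS distribution, the dropout rate and the local alpha are all assumptions, and the documents cannot place the trial within the range. The gains are conditional on the test being reached. ASAS40 and its sample size are unaffected.

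**What to change.** For ASDAS <2.1 only, add baseline ASDAS as a continuous covariate to the logistic model in SAP 6.1.1, 6.10.2 and Table RHBW.6.5, and keep the Fisher's exact fallback. State how a missing baseline ASDAS is handled so that no randomised patient leaves the analysis; one option is to use the mean over all arms. The odds ratio becomes conditional on baseline ASDAS, so report the response-rate difference with its confidence interval beside it and say whether that difference is adjusted. As a minor tidy-up, name the baseline value in the SAP 6.1.1 categorical MMRM for this endpoint, in line with protocol 9.2.1 and SAP 6.2.

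Timing decides its status. The SAP revision history places Version 3 before the first unblinding in June 2018, so the covariate could replace the prespecified model only in Version 3 or earlier. In Version 4 (28 February 2019) or later, report it as a labelled sensitivity analysis and leave the prespecified test in control of alpha. No change is needed for endpoints outside alpha control.

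The cost is one model term and a few sentences, with no new data; after unblinding, it is one extra output.
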